3.2 Exclusion Criteria

- 3.2.1 Known intolerance or hypersensitivity to Everolimus or other rapamycin analogs (e.g. sirolimus, temsirolimus).
- 3.2.2 Concomitant use of medications known to have strong inhibition or induction of CYP3A enzymes is discouraged and should be discussed with the study PI (see Table 4-7 and 4-8 for a list of prohibited medications). Note that systemic corticosteroids (e.g., dexamethasone is a CYP3A inducer) are not allowed. Inhaled corticosteroids are allowed.
- 3.2.3 Known impairment of gastrointestinal (GI) function or GI disease that may significantly alter the absorption of oral Everolimus.
- 3.2.4 Uncontrolled diabetes mellitus as defined by HbA1c > 8% despite adequate therapy. Patients with a known history of impaired fasting glucose or diabetes mellitus (DM) may be included, however blood glucose and antidiabetic treatment must be monitored closely throughout the trial and adjusted as necessary per standard of care.

3.2.5 Patients who have any severe and/or uncontrolled medical conditions such as:

- 3.2.5.1 Unstable angina pectoris, symptomatic congestive heart failure, myocardial infarction ≤6 months prior to start of Everolimus
- 3.2.5.2 Serious uncontrolled cardiac arrhythmia, or any other clinically significant cardiac disease.
- 3.2.5.3 Symptomatic congestive heart failure of New York Heart Association Class III or IV
- 3.2.5.4 Active (acute or chronic) or uncontrolled severe infection,
- 3.2.5.5 Liver disease such as cirrhosis, decompensated liver disease, and chronic hepatitis
- 3.2.5.6 Known severely impaired lung function (spirometry and DLCO 50% or less of normal and O₂ saturation 88% or less at rest on room air)
- 3.2.5.7 Active bleeding diathesis

3.2.6 Known history of HIV sero-positivity.

3.2.7 Patients who have received live attenuated vaccines within 1 week of start of everolimus and during the study. Patient should also avoid close contact with others who have received live attenuated vaccines. Examples of live attenuated vaccines include intranasal influenza, measles, mumps, rubella, oral polio, BCG, yellow fever, varicella and TY21a typhoid vaccines.

3.2.8 Patients who have a history of another primary malignancy, with the exceptions of: non-melanoma skin cancer, and carcinoma in situ of the cervix, uteri, or breast from which the patient has been disease free for ≥3 years.

3.2.9 Patients with a history of non-compliance to medical regimens or who are considered potentially unreliable or will not be able to complete the entire study.

3.2.10 Patients who are currently part of or have participated in any clinical investigation with an investigational drug within 1 month prior to dosing.

3.2.11 Pregnant or nursing (lactating) women.

3.2.12 Women of child-bearing potential (WOCBP), defined as all women physiologically capable of becoming pregnant, unless they are using highly effective methods of contraception during dosing of study treatment. Women of childbearing potential should be advised to use a highly effective method of contraception while receiving everolimus, and for up to 8 weeks after ending treatment. Highly effective contraception is defined as either:

- Total abstinence: When this is in line with the preferred and usual lifestyle of the subject. [Periodic abstinence (e.g., calendar, ovulation, symptothermal, post-ovulation methods) and withdrawal are not acceptable methods of contraception]
- Sterilization: have had surgical bilateral oophorectomy (with or without hysterectomy) or tubal ligation at least six weeks before taking study treatment. In case of oophorectomy alone, only when the reproductive status of the woman has been confirmed by follow up hormone level assessment
- Male partner sterilization (with the appropriate post-vasectomy documentation of the absence of sperm in the ejaculate). [For female subjects on the study, the vasectomized male partner should be the sole partner for that subject].
- Use of a combination of any two of the following (a+b or a+c or b+c):
 - a. Use of oral, injected, implanted or other hormonal methods of contraception
 - b. Placement of an intrauterine device (IUD) or intrauterine system (IUS)

- c. Barrier methods of contraception: Condom or Occlusive cap (diaphragm or cervical/vault caps) with spermicidal foam/gel/film/cream/vaginal suppository
- In case of use of oral contraception women should have been stable on the oral agent before taking study treatment.

3.2.13 Contraception Use

- During the course of the clinical trial, sexually active males must use a condom during intercourse while taking the drug and should not father a child in this period and for up to 8 weeks after stopping treatment.
- A condom is required to be used also by vasectomized men in order to prevent delivery of the drug via seminal fluid.
- Female partners of male patients must also be advised to use one of the following contraception methods: Use of (1) oral, injected, implanted or other hormonal methods of contraception, or (2) intrauterine device (IUD) or intrauterine system (IUS), or (3) prior male/female sterilization.
Female patients of childbearing potential must have a negative beta-human chorionic gonadotropin (β -hCG) pregnancy test at time of screening (urine or serum test is acceptable however, positive urine tests must be confirmed with serum testing)

3.2.14 Screening for hepatitis B:

Prior to start of Everolimus, the following three categories of patients should be tested for hepatitis B viral load and serologic markers, that is, HBV-DNA, HBsAg, HBs Ab, and HBc Ab.

- 3.2.14.1 All patients who currently live in (or have lived in) Asia, Africa, Central and South America, Eastern Europe, Spain, Portugal and Greece.
[<http://wwwnc.cdc.gov/travel/yellowbook/2012/chapter-3-infectious-diseases-related-to-travel/hepatitis-b.htm>]

3.2.14.2 Patients with any of the following risk factors:

- known or suspected past hepatitis B infection,
- blood transfusion(s) prior to 1990,
- current or prior IV drug users,
- current or prior dialysis,
- household contact with hepatitis B infected patient(s),
- current or prior high-risk sexual activity,
- body piercing or tattoos,
- mother known to have hepatitis B
- history suggestive of hepatitis B infection, e.g., dark urine, jaundice, right upper quadrant pain.
- Additional patients at the discretion of the investigator

3.2.14.3 Screening for hepatitis C: Patients with any of the following risk factors for hepatitis C should be tested using quantitative RNA-PCR:

- known or suspected past hepatitis C infection (including patients with past interferon 'curative' treatment),
- blood transfusions prior to 1990,
- current or prior IV drug users,
- current or prior dialysis,
- household contact of hepatitis C infected patient(s),
- current or prior high-risk sexual activity,
- body piercing or tattoos.

3.2.14.4 At the discretion of the investigator, additional patients may also be tested for hepatitis C.

4.0 TREATMENT PLAN

4.1 Treatment Dosage and Administration

The investigational treatment is Everolimus; it will be administered in conjunction with best supportive care. Best supportive care includes all care provided to patients deemed necessary by the treating physician, such as analgesics and anti-diarrheal therapies.

- Everolimus will be administered by mouth at a starting dose of 4.5 mg/m²/day. Each course of therapy will last for 28 days for up to 24 courses.
- The starting dose 4.5 mg/m² of Everolimus will be titrated upward (or downward), subject to tolerability, with the objective of achieving trough Everolimus levels in the range of 5-15 ng/mL.
- All dosages prescribed and dispensed to the patient and all dose changes during the study must be recorded.
- Medication labels will comply with US legal requirements and be printed in English. Additional labels may be used in the primary language of the study participant. They will supply no information about the patient. The storage conditions for Everolimus will be described on the medication label.

4.2 Treatment Assignment

This is a single arm, open label, phase II study of Everolimus for children with recurrent or progressive ependymomas.

Dosing Regimen

The investigator should promote adherence by instructing the patient to take the study drug exactly as prescribed and by stating that compliance is necessary for the patient's safety and the validity of the study. The patient should be instructed to contact the investigator if he/she is unable for any reason to take the study drug as prescribed.

4.3 Medication Formulations, Dosage and Administration

- 4.3.1 Everolimus is supplied by Novartis. Everolimus should be administered orally, once daily at the same time every day either consistently with food or consistently without food. Everolimus is available as dispersible tablets.
- 4.3.2 The dose of Everolimus is 4.5 mg/m²/day administered once a day. The initial calculated dose of Everolimus will be rounded either up or down to the nearest possible dose based upon available Dispersible Tablets (see section 4.4.3 below).
- 4.3.3 Everolimus will be supplied in the form of Dispersible Tablets (also referred to as 'tablets for oral suspension'): 2 mg, 3 mg and 5 mg.
- 4.3.4 Everolimus may be administered by either of the following two methods:
- 4.3.5 **Method 1, Using an oral syringe:** The required number of dispersible tablets (maximum of five 2 mg tablets, three 3 mg tablets, or two 5 mg tablets) should be placed into a 10 mL oral syringe. The plunger should be inserted and pushed inward to make contact with the dispersible tablet(s). A sufficient volume of water (approximately 5 mL) should be drawn up from a glass to cover the dispersible tablet(s). In addition, approximately 4 mL of air should be drawn up into the oral syringe. The filled oral syringe should be placed in a glass (tip up) and the contents left to disintegrate for 3 minutes. Prior to administration, the oral syringe should be inverted gently five times. While holding the oral syringe in an upright (tip up) position, excess air should be removed carefully. The full contents of the oral syringe should be immediately dispensed into the mouth of the patient, slowly and gently. The same volume of water and air should then be drawn up into the oral syringe, and the contents should be swirled to suspend any remaining particles. The contents should be administered as previously described to ensure the entire dose is administered.
- 4.3.6 **Method 2, Using a small drinking glass:** The required number of dispersible tablets (maximum of five 2 mg tablets, three 3 mg tablets, or two 5 mg tablets) should be placed into a small drinking glass (maximum size 100 mL) containing approximately 25 mL of water. The tablets should be left to disintegrate for 3 minutes. The contents should be stirred gently with a spoon, immediately prior to drinking. The glass should be rinsed with the same volume of water and stirred with the same spoon to suspend any remaining tablet particles. The rinse should be swallowed to ensure the entire dose is administered.
- 4.3.7 If vomiting occurs, no attempt should be made to replace the vomited dose. Patients should be instructed that if they miss a dose on one day, they must not take any extra dose the next day, but instead to immediately contact the study center as soon as possible to ask for advice.

4.4 Medication Supply and Accountability

4.4.1 Supplier: Everolimus tablets are supplied by Novartis and distributed through Biologics. Do not use commercial supply.

4.4.2 Agent Ordering: Sites will be provided the information for ordering drug supplies in the Study Procedures Manual.

4.4.3 Agent Accountability: The investigator is responsible for study medication accountability, reconciliation, and record maintenance. In accordance with local regulatory requirements, the investigator, designated site staff, or head of the medical institution (where applicable) must document the amount of investigational product dispensed and/or administered to study subjects, the amount returned by study subjects (if applicable), and the amount received from and returned to Biologics, when applicable. Product accountability records must be maintained throughout the course of the study.

After completion of the study, a final inventory of accountability records and unused study medications will be performed by the study monitor and site personnel. A record of the number of tablets dispensed to and returned by each subject at each visit must be maintained and reconciled with the study medication and compliance records in the eCRF. The cause of any missed doses should be discussed and documented.

Any AE(s) associated with missed doses must be recorded in the eCRF. Subjects should be instructed for the importance of compliance to study treatments.

An example study drug diary log is included in the protocol in Appendix III.

4.5 Recommended Dose of Everolimus

The recommended starting dose is 4.5 mg/m²/dose, once daily. Continue treatment for up to 2 years, until disease progression or unacceptable toxicity occurs. After 2 years of therapy, patients will complete the study protocol, but may continue therapy using commercially available drug based upon the clinical judgment of their treating physician and the child's parents or guardians.

4.5.1 Dose modification and dose delay

4.5.1.1 Therapeutic drug monitoring: Therapeutic drug monitoring of Everolimus blood concentrations is required for patients enrolled on study and taking Everolimus. Testing is to be performed by Quest Diagnostics using a validated bioanalytical LC/MS method (test code 18883X). Trough concentrations should be assessed 2 weeks (+/- 4 days) after the initial dose, after any change in dose or formulation, after an initiation or change in co-administration of CYP3A4 inducers or inhibitors, or after any change in hepatic status.

4.5.1.2 Dosing modifications:

Titrate the dose to attain trough concentrations of 5 to 15 ng/mL.

- For trough concentrations less than 5 ng/mL, increase the daily dose by 2 mg and repeat trough concentration in 2 weeks (+/- 4 days).
- For trough concentrations greater than 15 ng/mL, reduce the daily dose by 2 mg and repeat trough concentration in 2 weeks (+/- 4 days).
- The lowest possible dose level of Everolimus is 2 mg daily.
- If dose reduction is required for patients receiving the lowest available strength, administer every other day.

- For patients who do not tolerate the protocol-specified dosing schedule, dose adjustments are permitted in order to allow the patient to continue the study treatment. Dose levels are as follows: Level -2 = 3 mg/m²/dose, Level -1 = 3.8 mg/m²/dose, Level 0 = 4.5 mg/m²/dose, Level +1 = 5.2 mg/m²/dose and Level +2 = 6 mg/m²/dose. If dose adjustments need to be made for toxicity, patients' doses of Everolimus should not be targeted to achieve a trough level of 5 – 15 ng/mL.

Table 4-1**Dosing guidelines for Everolimus-related non-hematologic toxicities**

Toxicity	Action
Non-Infectious Pneumonitis	Please refer to Table 4-3.
Reactivation of HBV or HCV flare	Please refer to Table 4-5.
AST or ALT elevation	Maintain current dose level
Grade 1 (> ULN - 3.0 x ULN)	
Grade 2 (> 3.0 - 5.0 x ULN)	
AST or ALT elevation Grade 3 (> 5.0 - 20.0 ULN)*	Interrupt Everolimus administration until resolution to ≤ grade 1 (or ≤ grade 2 if baseline values were within the range of grade 2). If resolution occurs ≤ 7 days, Everolimus should be re-started at the dose level prior to interruption. If resolution takes > 7 days, or if event recurs within 28 days, hold Everolimus until recovery to ≤ grade 1 or baseline grade / value and reintroduce Everolimus at one dose level lower, if available.
AST or ALT elevation Grade 4 (> 20 x ULN)*	Interrupt Everolimus administration until resolution to ≤ grade 1 (or ≤ grade 2 if baseline values were within the range of grade 2). If resolution occurs ≤ 7 days, Everolimus should be re-started at one dose level lower. If resolution takes > 7 days, discontinue Everolimus.
Recurrence of Grade 4 AST or ALT elevation after dose reduction or toxicity requiring Everolimus interruption for > 28 days	Discontinue Everolimus.
Intolerable grade 2 mucositis, or grade 3 AE, except hyperglycemia or hypertriglyceridemia or hypercholesterolemia	Interrupt Everolimus administration until resolution to ≤ grade 1 or baseline grade / value. If resolution occurs within ≤ 7 days, Everolimus should be re-started at the dose level prior to interruption. If resolution takes > 7 days, or if event recurs within 28 days, hold Everolimus until recovery to ≤ grade 1 or baseline grade / value and reintroduce Everolimus at one dose level lower, if available. Patients will be withdrawn from the study if they fail to recover to ≤ grade 1 or baseline grade / value within 28 days.
Any other grade 4	Hold Everolimus until recovery to grade ≤ 1 or baseline value Reintroduce Everolimus at one dose level lower, if available.
Grade 3 or 4 clinical liver failure (asterixis or encephalopathy/coma)	Discontinue Everolimus
Recurrence of intolerable grade 2 mucositis or grade 3 event after dose reduction	Reduce dose to the next lower dose level, if available. The lowest possible dose level of Everolimus is 2 mg daily. Below this level, Everolimus must be discontinued.
Recurrence of grade 4 after dose reduction	Discontinue Everolimus
Any non-hematologic toxicity requiring Everolimus interruption for > 28 days	Discontinue Everolimus

* Should HCV flare be confirmed, the guidelines for flare must take precedence (Table 4-4).

Table 4-2**Dosing guidelines for Everolimus-related hematologic toxicities**

Toxicity	Action
Grade 2 thrombocytopenia (platelets <75, \geq 50x109/L)	Interrupt Everolimus until resolution to grade \leq 1 If resolution occurs \leq 7 days, reintroduce Everolimus at the dose level prior to interruption. If resolution occurs $>$ 7 days, or event occurs within 28 days, reintroduce Everolimus at one dose level lower, if available.
Grade 3 thrombocytopenia (platelets <50, \geq 25 x109/L)	Interrupt Everolimus until resolution to grade \leq 1 If resolution occurs \leq 7 days, reintroduce Everolimus at the dose level prior to interruption. If resolution occurs $>$ 7 days, or event occurs within 28 days, reintroduce Everolimus at one dose level lower, if available.
Grade 4 thrombocytopenia (platelets < 25 x109/L)	Interrupt Everolimus until recovery to grade \leq 1. Then reintroduce Everolimus at one dose level lower, if available.
Grade 3 neutropenia or anemia (neutrophil <1, \geq 0.5 x109/L)	Interrupt Everolimus until resolution to grade \leq 2 or baseline value If AE resolution occurs \leq 7 days, reintroduce Everolimus at the same dose level. If AE resolution occurs $>$ 7 days, or event occurs within 28 days, reintroduce Everolimus at one dose level lower, if available.
Grade 4 neutropenia or anemia	Interrupt Everolimus until recovery to grade \leq 2 or baseline value. Reintroduce Everolimus at one dose level lower, if available.*
Grade 3 febrile neutropenia	Interrupt Everolimus until resolution to grade \leq 1 (or baseline value) and no fever. Reintroduce Everolimus at one dose level lower, if available.*
Grade 4 febrile neutropenia	Discontinue treatment
Recurrence of grade 3 toxicity after dose reduction	Reduce dose to the next lower dose level, if available. The lowest possible dose level of Everolimus is 2 mg daily. Below this level, Everolimus must be discontinued.
*Recurrence of grade 4 toxicity (including febrile neutropenia) after dose reduction	Discontinue Everolimus
*Any hematologic toxicity requiring Everolimus interruption for $>$ 28 days	Discontinue Everolimus

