1.4 Rational for Targeted Dose

A concern regarding the use of Everolimus in oncology is the potential for immunosuppression during treatment. Consequently, in addition to individualizing the Everolimus dose according to the patient's body surface area, this protocol requires the upward titration of the dose from 4.5 mg/m², subject to tolerability, with the objective of achieving trough Everolimus levels in the range of 5-15 ng/mL. This range is based on the Phase II data from a TSC study conducted at the Cincinnati Children's Hospital Medical Center.²⁴ In this study, patients were treated with Everolimus from a starting dose of 3 mg/m² with subsequent upward titration to attain a RAD001 trough in the range 5-15 ng/mL. This regimen was efficacious (35% of patients had >50% shrinkage at 6 months) and showed acceptable tolerability. The starting dose of 4.5 mg/m² is based upon separate data from a phase I pediatric oncology study concluded that the maximum tolerated dose of everolimus in children is 5 mg/m²/day.²⁵ In order to optimize patient safety, and to ensure that excessive exposure does not occur, trough concentrations will be assessed initially and monitored as appropriate throughout the study.

Pharmacokinetics of RAD001 in patients with TSC:

During Study RAD001M2301, in patients with TSC who have SEGA, pre-dose (C_{min}) and 2-hour post-dose (C_{2h}) PK blood samples were collected at steady-state. Ages of patients in the Everolimus arm of study ranged from 1 to 23.9 years. Patients in this study received a starting dose of 4.5 mg/m²/day which was subsequently titrated to a whole blood trough concentration of 5-15 ng/mL. This is the starting dose and trough range approved for this indication.

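### Trough titration in flat 2 mg steps runs past the top dose level of 6 mg/m², where a reduction by one dose level has no single meaning, and Section 4.6.2 sets a different step for the same troughs

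*Combined protocol and SAP*

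**What the plan says.** Section 4.1 sets the start: "Everolimus will be administered by mouth at a starting dose of 4.5 mg/m²/day". Section 1.4 gives its basis: "The starting dose of 4.5 mg/m² is based upon separate data from a phase I pediatric oncology study", which concluded that "the maximum tolerated dose of everolimus in children is 5 mg/m²/day". The same section says "this protocol requires the upward titration of the dose from 4.5 mg/m², subject to tolerability", towards a trough of 5 to 15 ng/mL. It names monitoring as the safeguard: "to ensure that excessive exposure does not occur, trough concentrations will be assessed initially".

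Section 4.5.1.2 makes this operational. For a trough below 5 ng/mL, sites are to "increase the daily dose by 2 mg and repeat trough concentration in 2 weeks"; above 15 ng/mL they take off 2 mg. No maximum in mg, in mg/m² or in number of steps is given there. The section then lists five dose levels in mg/m²: 3, 3.8 and 4.5, followed by "Level +1 = 5.2 mg/m²/dose and Level +2 = 6 mg/m²/dose".

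Tables 4-1, 4-2 and 4-3 reduce for toxicity by one dose level. Table 4-5 (hepatitis B reactivation) reduces by one dose. Section 4.6.2 gives an increase of 33% below 5 ng/mL and a decrease of 25% above 15 ng/mL. Sections 4.3.5 and 4.3.6 limit the tablets per syringe or glass, to at most 10 mg of a single strength.

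**The concern.** Titration moves in milligrams and toxicity reduction moves in mg/m² levels, and nothing links the two scales. A flat 2 mg is a large step for a small child and a modest one for a large adolescent. A child following the titration rule can therefore reach a dose that is not on the list of levels. If that child then has toxicity, the tables send the site back to a list that does not contain the current dose.

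Two sites could both follow the protocol and give different doses after the same event. Tolerability is a secondary objective (Section 2.2.2), recurrence after a reduction can lead to discontinuation (Tables 4-1 and 4-2), and permanent discontinuations count toward stopping the study (Section 7.6). With 18 patients, a few inconsistent reductions could affect those results. The same reader also finds a maximum tolerated dose in Section 1.4 that one upward step exceeds, with no statement of how the two fit together.

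**Working it through.** **Inputs from the protocol.** Start 4.5 mg/m²/day (Section 4.1); step +2 mg (4.5.1.2); cited maximum tolerated dose 5 mg/m²/day (1.4); top level 6 mg/m² (4.5.1.2); tablets of 2, 3 and 5 mg, with the initial dose rounded to the nearest possible dose (4.3.2, 4.3.3). Combinations of these strengths make every whole mg from 2 upward.

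**Assumption.** The documents give ages 2 to 21 years but no BSA. I take 0.5 to 2.3 m² and show the break points so that the range can be checked.

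**Without rounding.** Dose after k steps = 4.5 + 2k/BSA mg/m².
- One step exceeds 5 when 2/BSA > 0.5, that is, BSA < 4.0 m².
- One step exceeds 6 when 2/BSA > 1.5, that is, BSA < 1.33 m².
- Two steps exceed 6 when 4/BSA > 1.5, that is, BSA < 2.67 m².

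**With rounding.** Start = nearest whole mg to 4.5 × BSA; then add 2 or 4 mg and divide by BSA.

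| BSA (m²) | Start, mg (mg/m²) | One step | Two steps | 6 mg/m² in mg |
|---|---|---|---|---|
| 0.6 | 3 (5.0) | 5 (8.33) | 7 (11.67) | 3.6 |
| 0.8 | 4 (5.0) | 6 (7.5) | 8 (10.0) | 4.8 |
| 1.0 | 4 or 5 (4.0 or 5.0) | 6 or 7 (6.0 or 7.0) | 8 or 9 (8.0 or 9.0) | 6.0 |
| 1.73 | 8 (4.62) | 10 (5.78) | 12 (6.94) | 10.4 |
| 2.0 | 9 (4.5) | 11 (5.5) | 13 (6.5) | 12.0 |
| 2.3 | 10 (4.35) | 12 (5.22) | 14 (6.09) | 13.8 |

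At BSA 1.0 the calculated start is exactly 4.5 mg, a tie that the protocol lets a site round either way.

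Over 0.5 to 2.3 m² in steps of 0.001, one step gives 5.21 to 8.99 mg/m² and two steps give 6.09 to 12.59. One step is above 6 at every BSA below about 1.17 m² (7/1.167 = 6.0), except at 1.0 when the tie is rounded down, and at some values up to just under 1.50 m². The two-step statement can first fail at about 2.33 m² (a 10.5 mg tie rounded down: 14/2.333 = 6.0) and next at 2.50 m² (15/2.5 = 6.0).

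**Reducing by one level from an off-list dose.** At BSA 0.8 and 8 mg (10 mg/m²), undoing one step gives 6 mg, a cut of 2/8 = 25%. Going to Level +2 gives 0.8 × 6 = 4.8, about 5 mg, a cut of 3/8 = 37.5%. At BSA 2.0 and 13 mg the order reverses: undoing one step gives 11 mg, while Level +2 is 12 mg.

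**The two trough rules.** From the unrounded start, +33% gives 4.5 × 1.33 = 5.99 mg/m², close to Level +2 at any BSA. The two increases agree only near 2/0.33 = 6.1 mg. From 4 mg (BSA 0.8) the rules give 6 mg and 5.3 mg; from 9 mg (BSA 2.0) they give 11 mg and 12.0 mg.

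**If the tablet limit were a daily limit.** With a 10 mg daily maximum, one step would not exceed 5 mg/m² at BSA of 2.0 m² or more, and two steps would not exceed 6 mg/m² at about 1.67 m² or more. The text presents the limit as a preparation instruction.

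**The case against.** The strongest reply is that this is deliberate exposure-guided dosing. Section 1.4 uses the 5 mg/m² figure to justify the starting dose, requires upward titration subject to tolerability, and cites a tuberous sclerosis study with the same start and trough range. Levels +1 and +2 are themselves above 5 mg/m². Increases stop once the trough reaches 5 ng/mL, doses come down above 15 ng/mL, and the trough is repeated after each change. Once a dose is adjusted for toxicity, Section 4.5.1.2 says it should no longer be targeted to the trough. All of this stands.

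A reader might therefore infer too much: that every child is taken above the maximum tolerated dose, that nothing restrains the increases, or that passing 5 mg/m² is in itself a protocol error. The documents do not support these readings. Only a child with a trough below 5 ng/mL who is stepped up from the start is affected, and the documents do not say how many that will be. What is absent is a stated mg/m² ceiling, not every restraint.

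It can also be said that the percentage rule belongs to drug interactions, since it sits in Section 4.6.2. But its bullets are worded for any low or high trough. Section 4.5.1.1 also calls for a trough after a change in CYP3A4 inducers or inhibitors, and Section 4.5.1.2 makes no exception for those patients. Placement alone does not settle which rule applies.

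None of these replies says what a one-level reduction means above 6 mg/m². The rule that ends trough targeting after toxicity governs later titration; it does not fix the size of the first reduction.

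**Conclusion.** The point holds as an inconsistency between dose rules, not as a finding that the titration target is wrong. For a child stepped up from the start, one step gives 5.2 to 9.0 mg/m² and two give 6.1 to 12.6. The protocol's own rule therefore leads off its list of levels, after one step in most small children and after two at every assumed BSA. From there, a one-level reduction has at least two defensible readings, which differ by about 1 mg in the examples above. Section 4.6.2 adds a second step size for the same thresholds, and Section 1.4 does not explain how titration relates to the maximum it cites.

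The sizes rest on the assumed BSA range and whole-mg rounding. The two-step statement could fail for a patient at or above about 2.33 m². The gap in the reduction rule does not depend on the exact range; it needs only one child titrated above 6 mg/m².

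**What to change.** Reconcile, in one amendment, Section 1.4, the titration bullets and dose levels in Section 4.5.1.2, the trough rules in Section 4.6.2, and the reduction wording in Tables 4-1, 4-2, 4-3 and 4-5. After the edit:

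- one titration scheme should apply to a given trough result, or the text should say which patients each scheme covers;
- a reduction from a trough-titrated dose, including one above 6 mg/m², should have one meaning in all four tables;
- Section 1.4 should state how the titration relates to the maximum tolerated dose it cites;
- Sections 4.3.5 and 4.3.6 should say whether the tablet maximum per preparation is also a daily limit.

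The sponsor chooses all values; no dose, step or limit is proposed here. The cost is a short text amendment, with no added patients or procedures.
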